16.2 Statistical Design

Due to the lack of data to identify relevant biomarkers, the estimation of RR would be of interest. In each group, the response rates will be examined to see if there's any preliminary evidence to suggest further studies. This study will not utilize a formal statistical design.

For each biomarker category, the RR will be estimated by the number of patients who achieve a PR or better divided by the total number of evaluable patients in each cohort. Exact binomial 95% confidence intervals for these rates will be calculated.

16.22 Sample Size: A maximum of 30 evaluable patients will be accrued in cohort A and B and 60 patients in cohort C and D respectively. We anticipate accruing an additional 2 in cohort A and B and 3 in cohort C and D to account for ineligibility, cancellation, major treatment violation, or other reasons. Therefore, the maximum projected accrual is 190 patients (A: 32, B: 32, C: 63 and D: 63).

16.23 Accrual Rate and Study Duration: The anticipated accrual rate is 6 evaluable patients per month. Therefore, the accrual period for this pilot study is expected to be approximately 32 months. The final analysis can begin approximately 35 months after the trial begins, i.e. as soon as the last patient has been observed for 1 months and allowing 2 months for data entry.

16.24 Other considerations: Adverse events, quality/duration of response, and patterns of treatment failure observed in this study, as well as scientific discoveries or changes in standard care will be taken into account in any decision to terminate the study

16.3 Analysis Plan.

The analysis for this study is planned to start after data maturity has occurred. It is anticipated that the earliest date in which the result will be available via manuscript, abstract or presentation after the last registered patient has been followed for at least 1 month.

16.31 Primary Outcome Analyses:

Each cohort (A-D) will be evaluated separately and independently.

16.311 Definition:

The primary endpoint of this study is RR after 1 cycle of treatment. RR is defined as a binary variable. A success will be defined as patient who achieve a response of a PR or better using the IMWG criteria (Section 11.0) after one cycle of treatment. All patients meeting eligibility criteria who have signed a consent form, who complete at least one cycle of treatment and have successfully submitted biospecimens (pre and post treatment) will be evaluable for the endpoint.

Estimation: For each biomarker of interest, RR will be calculated by the number of successes divided by the total number of evaluable patients in each cohort.

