2.0 Goals

2.1 Primary Goal

To determine response rates (>=PR) of prospectively treated MM patients with one cycle of therapy containing a combination of an immunomodulator and dexamethasone.

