16.0 Statistical Considerations and Methodology

16.1 Overview:

This is a pilot study to determine the response rates (>PR) of the combination of an immunomodulator and dexamethasone in Multiple Myeloma (MM) patients of each clinically relevant biomarker. This combination will be evaluated in four cohorts: Cohort A (Smoldering MM), Cohort B (Newly Diagnosed MM), Cohort C (Relapsed/Refractory MM) and Cohort D (Relapsed on Len maintenance). This study will not utilize a formal statistical design but will focus more on estimation rather than hypothesis testing.

16.11 Primary Endpoint: The primary endpoint of this trial is to estimate (>PR) response rates (RR) after one cycle of treatment. Biomarkers of interest will be identified and categorized into clinically relevant groups (e.g. positive vs. negative) by evaluating baseline and post treatment (after cycle one) biospecimens. RR will be estimated within each biomarker.

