16.32 Secondary Outcome Analyses

16.321 Biomarkers and RR will be analyzed using logistic regressions to identify predictive biomarkers.

16.322 RR among African American (AA) patients and white MM patients will be evaluated after one cycle of treatment. Chi-Square (or Fischer Exact) test and 95% confidence intervals will be estimated to compared AA and white patients descriptively.

16.323 Correlation between the depth of hematological responses and biomarkers will be estimated. Logistic regressions and chi square (or Fischer exact) testing will be utilized.

16.33 Data & Safety Monitoring:

The principal investigator(s) and the study statistician will review the study at least twice a year to identify accrual, adverse event, and any endpoint problems that might be developing. The Mayo Clinic Cancer Center (MCCC) Data Safety Monitoring Board (DSMB) is responsible for reviewing accrual and safety data for this trial at least twice a year, based on reports provided by the MCCC Statistical Office.

Adverse Event Stopping Rules: (Each cohort will be analyzed separately) The stopping rules specified below are based on the knowledge available at study development. We note that the Adverse Event Stopping Rule may be adjusted in the event of either (1) the study re-opening to accrual or (2) at any time during the conduct of the trial and in consideration of newly acquired information regarding the adverse event profile of the treatment(s) under investigation. The study team may choose to suspend accrual because of unexpected adverse event profiles that have not crossed the specified rule below.

Accrual will be temporarily suspended to this study if at any time we observe events considered at least possibly related to study treatment (i.e. an adverse

event with attribute specified as “possible”, “probable”, or “definite”) that satisfy either of the following:

- If 3 or more out of the first 10 treated patients experience grade 4+ non-hematological toxicities
- If after the first 10 patients have been treated, 30% of patients experience grade 4+ non-hematologic toxicities

We note that we will review grade 5 adverse events deemed “unrelated” or “unlikely to be related”, to verify their attribution and to monitor the emergence of a previously unrecognized treatment-related adverse event.

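### The response rate for each biomarker category is divided by all evaluable patients in the cohort, not by the patients in that category (Sections 16.2 and 16.311)

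*Combined protocol and SAP*

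**What the plan says.** Section 16.11 (Primary Endpoint) has biomarkers sorted into clinically relevant groups, for example positive and negative, and states that "RR will be estimated within each biomarker". The formula appears in two places:

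- Section 16.2, for each biomarker category: the rate is "estimated by the number of patients who achieve a PR or better divided by the total number of evaluable patients in each cohort". The intervals around these rates are to be 95% exact binomial.
- Section 16.311, Estimation paragraph, for each biomarker of interest: "RR will be calculated by the number of successes divided by the total number of evaluable patients in each cohort".

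Throughout the plan a cohort is one of A to D, and Section 16.31 says "Each cohort (A-D) will be evaluated separately and independently". Section 16.311 defines an evaluable patient by eligibility, consent, at least one completed cycle and submitted specimens before and after treatment. Biomarker category plays no part in that definition.

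**The concern.** A response rate within a category needs that category's patients in the denominator. The two formula sentences name the cohort total instead, so the written rule conflicts with Section 16.11.

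This matters because Section 16.1 says the study "will focus more on estimation rather than hypothesis testing", and Section 16.2 says that in each group "the response rates will be examined to see if" there is preliminary evidence for further studies. The category rates and their intervals are therefore a main output. A programmer who followed the wording could report a difference between marker groups that reflects only group size, or could hide or reverse a real one.

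**Working it through.** **Inputs from the plan.** Evaluable patients: 30 each in A and B, 60 each in C and D (Section 16.22). Intervals: exact binomial, 95% (Section 16.2). The plan states no response rate or interval width. Its only figure tied to these denominators is the accrual, which reproduces: (30 + 2) + (30 + 2) + (60 + 3) + (60 + 3) = 190.

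**Assumptions.** The plan gives neither the size of any biomarker category nor its response rate. Those values below are illustrations.

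**What the formula can mean.** Let N be the evaluable patients in the cohort, m those in the category, x the responders in the category and X all responders in the cohort.

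1. Numerator limited to the category, denominator not: x/N = (x/m) × (m/N), the category rate times the category's share of the cohort.
2. Neither limited: X/N, the same value for every category of every marker.
3. Both limited: x/m, the intended rate. This needs the cohort total to be read as the category total.

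**Examples (Clopper-Pearson 95% intervals).**

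| Assumed data | Category denominator, x/m | Reading 1, x/N |
|---|---|---|
| N = 30, 9 of 15 positive respond | 60% (32.3–83.7) | 9/30 = 30% (14.7–49.4) |
| N = 60, unrelated marker: positive 6 of 15 | 40% (16.3–67.7) | 6/60 = 10% (3.8–20.5) |
| Same cohort: negative 18 of 45 | 40% (25.7–55.7) | 18/60 = 30% (18.8–43.2) |
| N = 60, real difference: positive 12 of 20 | 60% (36.1–80.9) | 12/60 = 20% (10.8–32.3) |
| Same cohort: negative 16 of 40 | 40% (24.9–56.7) | 16/60 = 26.7% (16.1–39.7) |

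Rows 2 and 3 show a false threefold difference. Rows 4 and 5 show the true order reversed. Under reading 2, the cohort in rows 2 and 3 gives (6 + 18)/60 = 40% (27.6–53.5) for every category.

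**False ratio for an unrelated marker.** With equal true rates and a share π in the smaller category, reading 1 gives a ratio of (1 − π)/π. That is 1.0 at a 50/50 split (no false difference), 2.3 at 30/70, 3 at 25/75, 4 at 20/80 and 9 at 10/90.

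**Coverage under reading 1.** This is the probability that the interval for x/N contains the category's true rate p, with x ~ Binomial(m, p):

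| N | m (share) | p = 0.4 | p = 0.5 | p = 0.6 |
|---|---|---|---|---|
| 30 | 6 (20%) | 0% | 0% | 0% |
| 30 | 15 (50%) | 39.0% | 15.1% | 2.7% |
| 30 | 21 (70%) | 80.0% | 66.8% | 52.4% |
| 30 | 27 (90%) | 95.3% | 93.6% | 92.5% |
| 60 | 12 (20%) | 0% | 0% | 0% |
| 60 | 30 (50%) | 4.8% | 0.8% | 0.0% |
| 60 | 42 (70%) | 53.3% | 43.9% | 23.6% |
| 60 | 54 (90%) | 92.2% | 93.2% | 91.2% |

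With the interval computed on m instead, the lowest coverage over the same grid is 95.6% (m = 42, p = 0.5).

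**The case against.** The best defence is that this is loose drafting. In Section 16.2 neither the numerator nor the denominator carries its own category limit; only the opening phrase can limit either. Reading 1 lets that phrase act on the numerator alone. Applied consistently, it gives reading 3, which is correct, or reading 2, which defeats the sentence's purpose. Sections 16.1 and 16.11 point towards reading 3, and the reference to each cohort may only mean that cohorts are not pooled. Section 16.311 speaks of biomarkers rather than categories. Under reading 1 the positive and negative rates would add up to the cohort rate, an anomaly that might be noticed. The secondary regressions, "Biomarkers and RR will be analyzed using logistic regressions to identify predictive biomarkers", would not show the false difference. This is a pilot, and no decision threshold is attached to the category rates.

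Part of this stands. The team may well intend reading 3, the coverage figures apply only under reading 1, and the damage is limited. It does not rescue the text. Both formula sentences name the cohort total, and nothing narrows the definition of evaluable. Reading 2 is also wrong. The different wording of Section 16.311 does not help: Section 16.11 uses the same term for the grouped estimate, and a cohort total would make every biomarker's rate identical. The secondary analyses do not correct the primary estimates.

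**Conclusion.** The concern holds: the stated rule for the category rates, taken literally, is wrong and conflicts with Section 16.11. Under reading 1 the reported rate is the true category rate multiplied by the category's share of the cohort, so a category holding 20% to 70% of the cohort is reported at 0.2 to 0.7 times its rate. Under reading 2 all categories show one rate. Under reading 3 there is no error, but the plan does not state that reading. The numerical illustrations rest on assumed category sizes and response rates.

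Not affected are the overall cohort rate that serves the primary goal ("To determine response rates (>=PR) of prospectively treated MM patients with one cycle of therapy"), the logistic regressions and chi-square or Fisher tests of Sections 16.321 to 16.323, and the accrual of 190. This should be fixed before analysis.

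**What to change.** In Section 16.2 and in the Estimation paragraph of Section 16.311, define the denominator as the number of evaluable patients in that biomarker category within that cohort, limit the numerator to responders in the same category, and compute the exact 95% interval on that number. Report the overall cohort rate (all responders over all evaluable patients in the cohort) as a separate line.

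The cost is two sentences, with no change to sample size, data collection or secondary analyses. Category intervals will generally be wider than those on the cohort total. With 9 of 15 responding, the half-width is (83.7 − 32.3)/2, about 26 percentage points. That is the correct width for a group of that size.

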4.0 Test Schedule

Tests and procedures	Active Monitoring Phase					
	Prior to registration		Prior to Day 1 Cycle 1	Prior to Day 1 Cycle 2	Prior to Day 1 Cycles 3-6	End of Treatment
	≤28 days	≤14 days				
Window				±3 days	±3 days	±7 days
Complete Medical History		X				
Physical exam, Wt, PS		X	X ³	X	X	X
Adverse event assessment		X		X	X	X
Pregnancy test ¹		X				
Height		X				
Hematology group: CBC with 5-part differential		X	X ³	X	X	X
Chemistry group to include serum creatinine, calcium, T.Bili, D. bili, AST, and ALT		X	X ³	X	X	X
LDH, Beta-2-microglobulin, Plasma cell assessment		X	X ³			
PT/PTT/INR		X				
TSH		X				
Electrophoresis of serum and urine		X	X ^{3,5}	X ⁵	X ⁵	X ⁵
Immunofixation or mass fixation of serum and urine		X		X ⁷	X ⁷	X ⁷
Affected Serum Immunoglobulin ²		X	X ³	X	X	X
Serum Immunoglobulin free light chain		X	X ³	X	X	X
WBLDCT ³ or PET/CT	X			X ³	X ³	
Bone marrow aspirate and biopsy	X					
Patient Medication Diary (Appendix II)			X	X	X	
Research bone marrow sample ^R	X			X ⁶		X ⁴
Research blood sample ^R	X			X ⁶		X ⁴

Cycle 1 = 21

Cycles 2-6 = 28 days

Footnotes on following page:

1. For women of childbearing potential only. Must be done ≤ 7 days prior to registration. If the urine test is positive or cannot be confirmed as negative, a serum pregnancy test will be required
2. Affected immunoglobulin refers to the baseline M-protein type, that is, IgG, IgA, or IgD. Not applicable if patient “non-secretory” or if patient has no heavy chain, i.e. light chain myeloma. Affected immunoglobulin is required after baseline only if it used for disease monitoring instead of SPEP (e.g. IgA myeloma).
3. Baseline then only if clinically indicated.
4. Optional BM sample submission for patients who discontinue treatment due to disease progression or relapse, intolerable AEs, patient refusal, subsequent treatment for myeloma.
5. Urine Electrophoresis required only if used to assess disease response
6. Bone marrow aspirate done at the end of Cycle 1 (prior to cycle 2) will be paid for by research.
7. Immunofixation (IF) only needed in absence of M-Spike to document CR or SCR

R Collected as part of the IRB# 521-93, IRB# 14-009163 and/or IRB# 919-04

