7.0 Protocol Treatment

7.1 Treatment Schedule

Cohort A and B Cycle 1

Treatment medication table. Patient may receive Lenalidomide OR Lenalidomide + Dexamethasone.

Agent	Dose Level	Route	Day	Re Rx
Lenalidomide	25 mg*	Oral	Cycle 1: Day 1-14	Cycle 1: 21 days
Dexamethasone	40 mg**	Oral	Cycle 1: Day 1 ,8, ,15	Cycle 1: 21 days

Cycle 1 length = 21 days

* Starting dose will be determined as per the creatine clearance below (see 7.12)

**The dose of dexamethasone used can be determined by the treating physician and omitted if needed.

Cohort C and D Cycle 1

Treatment medication table. Patient may receive Lenalidomide + Dexamethasone OR Pomalidomide + Dexamethasone.

Agent	Dose Level	Route	Day	ReRx
Lenalidomide	25 mg*	Oral	Cycle 1: Day 1-14	Cycle 1: 21 days
Pomalidomide	4 mg	Oral	Cycle 1: Day 1-21	Cycle 1: 21 days
Dexamethasone	40 mg**	Oral	Cycle 1: Day 1 ,8, ,15	Cycle 1: 21 days

Cycle 1 length = 21 days

* Starting dose will be determined as per the creatinine clearance below (see 7.12)

** The dose of dexamethasone used can be determined by the treating physician and omitted if needed.

Cohort A and B Cycles 2-6

Treatment Medication Table. Patient may receive Lenalidomide based regimens.

Agent	Dose Level	Route	Day	Re Rx
Lenalidomide	25 mg*	Oral	Cycle 2-6: Day 1-21	Cycles 2-6: 28 days
Dexamethasone	40 mg**	Oral	Cycle 2-6: Day 1 ,8, ,15, 22	Cycles 2-6: 28 days

Note: Standard of care agents can be added for cycles 2-6 as long as the regimen contains lenalidomide

Cycles 2-6 length = 28 days

* Any dose-adjustments will be determined as per the creatine clearance below (see 7.12).

** The dose of dexamethasone used can be determined by the treating physician and omitted if needed.

Cohort C and D Cycles 2-6

Treatment medication table. Patient may receive Lenalidomide based regimen OR Pomalidomide based regimen.

Agent	Dose Level	Route	Day	ReRx
Lenalidomide	25 mg*	Oral	Cycles 2-6: Day 1-21	Cycles 2-6: 28 days
Pomalidomide	4 mg	Oral	Cycles 2-6: Day 1-21	Cycles 2-6: 28 days
Dexamethasone	40 mg**	Oral	Cycle 2-6: Day 1,8,15,22	Cycles 2-6: 28 days

Note: Standard of care agents can be added for cycles 2-6 as long as the regimen contains lenalidomide or pomalidomide

Cycles 2-6 length = 28 days

* Any dose-adjustments will be determined as per the creatinine clearance below (see 7.12).

** The dose of dexamethasone used can be determined by the treating physician and omitted if needed.

7.12

Creatinine Clearance (CrCl)	Lenalidomide Dose

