11.4 Response and Progression

Criteria for response and progression are listed in Table 11.5. Progressive disease for all patients as defined in Table 11.5.

Table 11.5

STANDARD IMWG RESPONSE CATEGORY	RESPONSE CRITERIA ^a
Stringent Complete Response (sCR) ^b	
CR as defined plus
 
Normal FLC ratio and
 
 • Absence of clonal PCs by immunohistochemistry or 2- to 4- color flow cytometryⁱ
Complete Response (CR) ^b	
 • Negative immunofixation of serum and urine^c and • Disappearance of any soft tissue plasmacytoma and • <5% PCs in Bone Marrow and • If the only measurable disease is FLC, a normal FLC ratio^d • For patients with extramedullary plasmacytoma present at baseline: a) FDG-avid or PET positive prior to therapy: Mass of any size permitted if PET negative and b) Variably FDG-avid or PET negative: Regression to normal size on CT. For patients with only skin involvement, these same criteria apply to skin lesions measured with a ruler.
Very Good Partial Response (VGPR)	
 • Serum and urine M-protein detectable by immunofixation but not on electrophoresis^c or • ≥90% reduction in serum M-protein and urine M-protein <100 mg/24 h^c • If the only measurable disease is FLC, a >90% reduction in the difference between involved and uninvolved FLC levels • Not applicable for those patients who do not have a “measurable” serum M-spike, serum free light chain, or urine M-spike at baseline
Partial Response (PR)	
 • If present at baseline, ≥ 50% reduction of serum M-protein and reduction in 24-hour urinary M-protein by ≥90% or to <200 mg/24hrs^c • If the only measurable disease is FLC, a ≥50% reduction in the difference between involved and uninvolved FLC levels • If the only measurable disease is BM, a ≥ 50% reduction in BM PCs (provided the baseline PCs was ≥ 30%)

	
 • If present at baseline, $\geq 50\%$ reduction in the size (SPD) of soft tissue plasmacytomas ^j • For patients with extramedullary plasmacytoma present at baseline: $\geq 50\%$ decrease in SPD of up to 6 largest dominant masses and a) FDG-avid or PET positive prior to therapy: one or more PET positive at previously involved sites OR b) Variably FDG-avid or PET negative: regression on CT or by measurements with a ruler in patients with only skin involvement

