12.0 Descriptive Factors

- 12.1 Prior treatment: 0 vs 1 vs 2 vs 3+
- 12.2 Parameters followed for hematologic response: serum monoclonal protein ≥ 0.5 g/dL and urine monoclonal protein ≥ 200 mg/24 hours vs. serum monoclonal protein ≥ 0.5 g/dL only vs. urine monoclonal protein ≥ 200 mg/24 hours only vs. serum immunoglobulin free light chain ≥ 10 mg/dL vs. bone marrow plasma cells $\geq 30\%$ vs. measurable bone or extramedullary disease on imaging. Distinguish between SPEP measurements versus quantitative IgA measurements versus quantitative IgD measurements for serum monoclonal protein.
- 12.3 mSMART FISH risk level: high risk vs low risk vs unknown.

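### One-cycle response is scored by a different marker rule from patient to patient, and no analysis in Section 16 uses the marker type that the study already records

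*Combined protocol and SAP*

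**What the plan says.** **Endpoint and timing.** Section 16.311: "The primary endpoint of this study is RR after 1 cycle of treatment". Success is PR or better by the IMWG criteria. Section 7.1 gives "Cycle 1 length = 21 days" for all cohorts. The Section 4.0 schedule places the disease assessment at "Prior to Day 1 Cycle 2" with a window of ±3 days, so at about day 18 to 24.

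**PR rule (Table 11.5).** It depends on what is measurable at baseline:
- serum and urine M-protein: "If present at baseline, ≥ 50% reduction of serum M-protein and reduction in 24-hour urinary M-protein by ≥90% or to <200 mg/24hrs";
- FLC only: "If the only measurable disease is FLC, a ≥50% reduction in the difference between involved and uninvolved FLC levels";
- marrow only: at least a 50% fall in plasma cells.

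Section 11.1 confines the FLC criteria to patients who entered on FLC alone.

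**What is recorded.** Section 12.2 lists the followed parameter in six categories as a descriptive factor and adds: "Distinguish between SPEP measurements versus quantitative IgA measurements versus quantitative IgD measurements for serum monoclonal protein". Footnote 2 of Section 4.0 identifies the baseline heavy-chain type.

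**What is analysed.** Section 5.0 names cohort as the only grouping factor. Sections 16.2 and 16.311 give response rate (RR) by cohort and biomarker category. Section 16.321 says: "Biomarkers and RR will be analyzed using logistic regressions to identify predictive biomarkers". Section 16.322 compares African American (AA) and white patients, and Section 16.323 relates biomarkers to depth of response. None of them mentions marker type.

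**The concern.** A serum, urine or FLC level after treatment reflects both how far production has fallen and how much of the earlier protein has cleared. After several cycles clearance matters little. After one 21-day cycle it may decide whether a patient crosses the PR line. The urine threshold also differs from the others whatever the clearance.

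Two results are exposed. A cohort's RR will partly reflect its mix of marker types, which makes it harder to compare across cohorts or with other studies. And a biomarker that happens to be commoner in, say, light-chain disease than in IgG disease could appear to predict response to the immunomodulator when it only tracks the measuring scale. Finding predictive biomarkers is the purpose of Section 16.321.

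**Working it through.** **Plan's own figures.** The plan gives no number on this point. The cohort sizes used below come from Section 16.22: 30 evaluable in A and in B, 60 in C and in D. With the stated extras, 32 + 32 + 63 + 63 = 190, as the plan says. No alpha, power or effect size is stated.

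**Step 1: clearance and the day-21 reading.** Assumption, not in the documents: first-order clearance with half-life T, and a share k of production stopped on day 1. Then

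fall at day t = k × (1 − 2^(−t/T)), and a 50% fall at day 21 needs k ≥ 0.5 / (1 − 2^(−21/T)).

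| Assumed T | Largest fall at day 21 (k = 1) | k needed for a 50% fall |
|---|---|---|
| hours | about 100% | 0.50 |
| 6 days | 91% | 0.55 |
| 10 days | 77% | 0.65 |
| 15 days | 62% | 0.81 |
| 18 days | 56% | 0.90 |
| 21 days | 50% | 1.00 |
| 23 days | 47% | not reachable |

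At T = 21 days the window alone moves the largest possible fall from 45% (day 18) to 55% (day 24). For a fast-clearing urine protein judged by the 90% route, k must be about 0.90. By the other route a baseline of 250 mg/24 h needs only a little over (250 − 200)/250 = 20%. Urine therefore cannot be grouped with the 50% rules.

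If k were spread evenly over 0 to 1, RR would be 1 minus the k needed: about 10% at T = 18, 20% at T = 15, 35% at T = 10, and 50% at T of hours. This motivates the range of 10-35% (slow) against 50% (fast) used below.

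**Step 2: cohort RR.** With RR 20% (slow) and 50% (fast), cohort RR = 0.20 + 0.30 × fast share. Fast shares of 10%, 20%, 30% and 50% give 23%, 26%, 29% and 35%, with the same drug effect throughout.

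**Step 3: a biomarker with no effect within marker type.** Assumed mix: 60% slow, 40% fast. Worked case: RR 10% and 50%, biomarker prevalence 20% in slow and 60% in fast.
- Biomarker-positive share: 0.6 × 0.2 + 0.4 × 0.6 = 0.36. Fast share among positives: 0.24/0.36 = 0.667; among negatives: 0.16/0.64 = 0.25.
- RR in positives: 0.333 × 0.10 + 0.667 × 0.50 = 0.367. RR in negatives: 0.75 × 0.10 + 0.25 × 0.50 = 0.20.
- Crude OR: (0.367/0.633) / (0.20/0.80) = 2.3.

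False-positive rates by simulation (uncorrected chi-square at two-sided 0.05; Mantel-Haenszel when stratified):

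| RR slow / fast | Prevalence slow / fast | Crude OR | n = 60, crude | n = 30, crude | Stratified |
|---|---|---|---|---|---|
| 10 / 50% | 20 / 60% | 2.3 | 30-31% | 18% | 5% |
| 10 / 50% | 20 / 40% | 1.6 | 12-13% | 9% | 5% |
| 20 / 50% | 20 / 60% | 1.8 | 17-18% | 12% | 5% |
| 20 / 50% | 20 / 40% | 1.4 | 9% | 7% | 5% |
| 35 / 50% | 20 / 60% | 1.3 | 8% | 6-7% | 5% |
| 35 / 50% | 20 / 40% | 1.16 | 6% | 5-6% | 5% |
| any of these | 20 / 20% | 1.0 | 5% | 4-5% | 4-5% |

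Fisher's exact test lowers the top n = 60 figure to 24%. The last row shows that bias needs an association between biomarker and marker type.

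**The case against.** The strongest case against has five parts.

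1. **The half-lives come from outside.** This stands. The documents neither give nor discuss clearance. Without it, what remains is that the urine rule differs from the others and that marker type is unused.
2. **The biomarkers are not yet chosen, so no association with marker type can be shown.** This stands too. A reader might infer that the biomarker results are confounded; the documents support only that they can be. For a single-arm RR the issue is case mix, not confounding.
3. **PR is not uniformly a 50% fall read on day 21.** Correct. Urine has its own rule, the visit has a window, and Table 11.5 requires two consecutive assessments before new therapy. The second may fall in cycle 2, when Section 7.1 allows agents to be added; those passages need to be reconciled.
4. **This is an estimation-only pilot with wide intervals.** Exact 95% intervals are 14.7-49.4% for 9/30 and 18.8-43.2% for 18/60, and no significance threshold is set. True, but bias moves an estimate as well as a test, and Section 16.321 sets out to identify predictive biomarkers. Section 16.321 also does not forbid covariates, but one chosen after the data are seen carries less weight than a preset one.
5. **Stratifying strains small cohorts.** This limits the fix. Six marker categories are too many for 30 patients. With about 29 AA patients in all (15% is 4-5 in A or B and 9 in C or D), the race comparison cannot be split by marker within cohort.

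**Conclusion.** The point holds as a risk that the analysis plan leaves open, not as a demonstrated bias. From the documents alone: PR after one 21-day cycle is scored on different criteria by followed marker, marker and heavy-chain type are recorded, and no analysis in Section 16 uses them.

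The size rests on assumptions: half-lives from hours to about 23 days, RR of 10-35% against 50%, a 60:40 mix, and biomarker prevalence of 20% against 40-60%. Under these, a null biomarker is falsely significant in about 6-31% of cohorts of 60 and 5-18% of cohorts of 30, against 4-5% when stratified. The top of each range is an adverse corner and should not be read as the expected rate; near the bottom the excess is negligible. A reader might also infer that IgG patients cannot reach PR in one cycle. In the model that follows only for half-lives beyond 21 days at a day-21 reading, which the documents do not establish.

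**What to change.** - **Section 16.311:** also tabulate each cohort's RR descriptively by collapsed followed marker: IgG followed by SPEP; other serum M-protein or FLC; and urine-only, marrow-only and imaging-only shown separately. Section 12.2 alone does not split SPEP-followed patients by heavy chain, so take that from the baseline type in Section 4.0, footnote 2.
- **Sections 16.321 and 16.323:** beside the unadjusted analysis, preset a supporting analysis with this collapsed factor as a stratum or covariate (Mantel-Haenszel, or exact or conditional logistic regression).
- **Section 16.322:** only report marker mix by race, or stratify with cohorts pooled.
- **No common-scale FLC analysis** across all patients, unless it is labelled exploratory and non-IMWG, because Section 11.1 restricts the FLC criteria to patients who entered on FLC alone.

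**Cost:** wording only, with no new samples or visits. Intervals widen somewhat, and strata in cohorts A and B will be sparse, so results there should be read as descriptive.
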